#### CONFIDENTIAL

- Severe laboratory abnormalities:
  - Neutrophil count  $\leq 0.5 \times 10^3/\mu L$
  - $\circ$  Platelet count  $\leq 50 \times 10^{3}/\mu L$
  - $\circ~$  ALT and/or AST values >3  $\times$  ULN with total bilirubin >2  $\times$  ULN, excluding confirmed Gilbert's Syndrome
  - $\circ$  Confirmed AST and/or ALT >5 × ULN (for more than 2 weeks)

#### 8.4.2.2. Reasons for Temporary Discontinuation of Study Drug

Study drug dosing will be temporarily discontinued in the event of:

- An infection that requires parenteral treatment with antibiotic, antifungal, antiviral, antiparasitic, or antiprotozoal agents, or requires oral treatment with such agents for longer than 2 weeks
- Other intercurrent illnesses that may or may not require treatment with some prohibited medications (eg, systemic immunosuppressive/immunomodulating drugs) or major surgery, which could, in the opinion of the investigator, present an unreasonable risk to the patient as a result of his/her continued participation in the study and receiving study drug

A decision to temporarily discontinue study drug and/or to reinstitute study treatment should be discussed with the medical monitor. The investigator may suspend study treatment at any time, even without consultation with the medical monitor if the urgency of the situation requires immediate action and if this is determined to be in the patient's best interest. However, the medical monitor should be contacted as soon as possible in any case of study drug discontinuation. Resumption of study treatment after temporary discontinuation requires consultation and agreement between the investigator and the medical monitor.

After the condition leading to temporary discontinuation of study drug resolves, study drug dosing may resume. A decision to temporarily discontinue study drug and/or resume study drug dosing should be discussed with the Regeneron Pharmaceuticals, Inc. medical monitor.

If a patient requires a prohibited medication at any time during the study, the principal investigator should contact the Regeneron medical monitor (except for illness requiring prompt treatment). Based on the discussions, study drug may be continued or temporarily or permanently discontinued.

## 8.5. Management of Acute Reactions

## 8.5.1. Acute Injection Reactions

#### 8.5.1.1. Systemic Injection Reactions

Emergency equipment and medication for the treatment of systemic reactions must be available for immediate use. All injection reactions must be reported as AEs (as defined in Section 10.2.1) and graded using the grading scales as instructed in Section 10.2.4.

CONFIDENTIAL

Regeneron Pharmaceuticals, Inc.

Acute systemic reactions following injection of study drug (SC) should be treated using clinical judgment to determine the appropriate response according to typical clinical practice.

## 8.5.1.2. Local Injection Site Reactions

Local injection site reactions must be reported as AEs and graded according to Section 10.2.4.

## 8.6. Method of Treatment Assignment

In Part A, approximately 90 patients will be randomized in a 1:1:1 ratio to receive higher or lower exposure dose arms of dupilumab (dose regimen according to the weight tier described in Section 8.1) or placebo according to a central randomization scheme provided by an IVRS/IWRS to the designated study pharmacist (or qualified designee). Randomization will be stratified according to weight at baseline ( $\geq$ 5 kg to <15 kg,  $\geq$ 15 kg to <30 kg, or  $\geq$ 30 kg to <60 kg).

# 8.7. Blinding

Study patients, the principal investigators, and study site personnel will remain blinded to all randomization assignments. For Parts A and B, study drug administration at the study sites will be performed only by injection personnel who will not perform any clinical assessment/procedures. During the conduct of Parts A and B, the blinded Regeneron medical/study director, study monitor, and any other Regeneron and contract research organization (CRO) personnel who are in regular contact with the study site will remain blinded to all patient randomization assignments.

If the primary analysis is performed on Part A data (see Section 6.2), Part A will be unblinded for selected sponsor study personnel while Part B is ongoing. The team performing the primary analysis will be separate from the ongoing study team. No study personnel involved in the day-to-day conduct of the study will have access to any unblinded data before the database is locked for Part B of this study. All participants will receive open-label dupilumab during Part C.

Blinded study drug kits coded with a medication numbering system will be used for the doubleblind (Part A) and extended active (Part B) treatment periods. In order to maintain the blind (until the database is locked for Part B), lists linking these codes with product lot numbers will not be accessible to individuals involved in study conduct. Part C study drug will be labeled with dupilumab.

During the double-blind (Part A) and extended active (Part B) treatment periods, anti-drug antibody, drug concentration results, any post-treatment tissue eosinophil counts and histologic results, and biomarker results (eotaxin-3 and total IgE) will not be communicated to the sites, and the sponsor's blinded study team will not have access to results associated with patient identification until after the database is locked for the respective study part.

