#### **3.2.2.** Rationale for Dose Selection

Based on the known safety, efficacy, and PK of dupilumab, which has been studied in adults, adolescents, and children as young as 6 months of age, the dose regimen to be investigated in this study in children with EoE aged  $\geq 1$  year to <12 years is weight-based dosing as follows:

Higher exposure dupilumab regimens for Parts A, B, and C (approximates Ctrough of mg QW regimen in adults):

Lower exposure dupilumab regimens for Part A and B (approximates Ctrough of mg Q2W regimen in adults):

- mg once every 4 weeks (Q4W) in patients who weigh  $\geq$ 5 kg to <15 kg
- mg Q4W in patients who weigh  $\geq 15$  kg to <30 kg
- mg Q2W in patients who weigh  $\geq$ 30 kg to <60 kg
- mg Q2W in patients who weigh  $\geq 60$  kg (Part B Only)

NOTE: Patients  $\geq 60$  kg are excluded from enrollment into Part A, but patients may reach this weight tier during the extended active period (Part B) or open label extension period (Part C). All patients will be reassigned a weight-tiered dose for the higher exposure dupilumab regimen in Part C at visit 17 / week 52 (or start of open label period for re-entry patients). At specified inclinic visits in Part C, patients that have increased in body weight to a higher weight tier will be re-assigned to an appropriate open-label treatment regimen for their corresponding weight.

During Part A and Part B, patients will receive dupilumab injections at the frequency of QW, Q2W, or Q4W with matching placebo alternating with dupilumab doses so the injection frequency will be identical within weight tiers for regimen-blinding purposes. Patients will remain within the originally assigned higher or lower dosing exposure arm throughout Part A and Part B.

For Part C, patients will receive the higher exposure dupilumab weight tiered dosing regimen. No matching placebo will be administered in Part C. The doses and regimens of dupilumab are intended to approximate the steady-state trough concentrations ( $C_{trough}$ ) observed in adult patients receiving  $\blacksquare$  mg QW for the higher exposure regimen. In order to achieve similar exposures across this broad age range, the doses will be assigned by weight tiers.

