## **11.4.9.** Timing of Statistical Analysis

The primary analysis may be performed when the last patient completes 16 weeks of treatment duration in Part A. No changes in the conduct of the study will be made based on this primary analysis. The assessment of primary and secondary endpoints specified in Section 4.1.1 and Section 4.1.2 will be analyzed descriptively in Part B as the final analysis. Part C will be described descriptively. Hence, there will be no need for alpha adjustment due to the primary analysis.

In order to maintain study integrity (with respect to the extended active treatment and posttreatment follow-up safety visits) in the event a decision is made to perform the primary analysis, a dissemination plan will be written. This plan will clearly identify the team (including the statistician) that will perform the primary analysis and all related activities, restrict other clinical team members and other sponsor personnel from access to individual patient treatment allocation and site level analysis results, and ensure that the dedicated team will not participate in the data review or data decisions for the following extended active treatment safety analyses.

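### Section 8.7 sets two release points: its last paragraph permits the sponsor's blinded team to see patient-identified Part A results at the Part A lock, while Part B may still be blinded

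*Protocol*

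**What the plan says.** Section 8.7 has four paragraphs that bear on who may know what, and when.

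- **First paragraph.** While Parts A and B are being conducted, the blinded medical/study director, the study monitor and other sponsor and CRO "personnel who are in regular contact with the study site will remain blinded to all patient randomization assignments".
- **Second paragraph.** If the primary analysis is performed, "Part A will be unblinded for selected sponsor study personnel while Part B is ongoing". A separate team does that analysis. "No study personnel involved in the day-to-day conduct of the study will have access to any unblinded data before the database is locked", and the sentence goes on to name the Part B lock.
- **Third paragraph.** The lists linking kit codes to product lots stay closed to those conducting the study until the Part B lock.
- **Last paragraph.** During both treatment periods, anti-drug antibody results, "drug concentration results, any post-treatment tissue eosinophil counts and histologic results, and biomarker results (eotaxin-3 and total IgE) will not be communicated to the sites". As for the blinded staff at the sponsor, they "will not have access to results associated with patient identification until after the database is locked for the respective study part".

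Section 11.4.9 says "The primary analysis may be performed when the last patient completes 16 weeks of treatment duration in Part A". In that event a dissemination plan must name the analysis team and "restrict other clinical team members and other sponsor personnel from access to individual patient treatment allocation", as well as from site-level results.

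Section 3.2.2 adds: "Patients will remain within the originally assigned higher or lower dosing exposure arm throughout Part A and Part B".

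**The concern.** The first three paragraphs of Section 8.7 point to one principle: those who run the study stay blinded until Part B is finished and locked. The last paragraph is the only place that deals by name with the patient-level results most likely to reveal treatment, and it uses a different and possibly earlier release point. If Part A is locked first, the blinded team is no longer barred by that paragraph from Part A concentrations and histology linked to patient identifiers while the same patients are still on blinded Part B treatment.

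At stake is the integrity of Part B. The protocol invests in that blind: placebo injections continue in Part B to mask the regimen (Section 8.1), the emergency-unblinding rules extend to Part B (Section 8.8), and the primary-analysis team is kept out of later data review and data decisions (Section 11.4.9). Sponsor medical staff are consulted on interrupting study drug and on prohibited medication (Sections 8.4.2.2 and 8.10.1). Part B safety is presented by exposure arm (Section 11.4.5), and the Part B efficacy summaries may include statistical tests (Section 11.4.3.2).

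**Working it through.** This is mainly a check of one passage against another. The only arithmetic is the allocation count.

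**1. Do the release points differ?**

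| Section 8.7 | Who | What is withheld | Until |
|---|---|---|---|
| Paragraph 1 | Site-contact sponsor and CRO personnel | All randomization assignments | During the conduct of Parts A and B |
| Paragraph 2 | Day-to-day study personnel | Any unblinded data | Part B lock |
| Paragraph 3 | Those conducting the study | Kit-code lists | Part B lock |
| Paragraph 4 | Sponsor's blinded study team | Patient-identified concentration, antibody, histology and biomarker results | Lock of the respective part |

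For Part B results, paragraph 4 agrees with the others. For Part A results it gives the Part A lock. The word 'respective' has a function only if the two parts can have different release points.

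**2. Can the Part A lock come before the Part B lock?** Yes, though it need not. Sections 6.2 and 11.4.9 make the week 16 analysis optional, and paragraph 2 of Section 8.7 foresees it while Part B is ongoing. Sections 1 and 3.3.1.1 already report the Part A primary result, so the analysis has been done. The document gives neither lock date.

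**3. Would the Part A results reveal assignment?** Table 1 schedules functional dupilumab samples at baseline, week 4 and week 16. The week 16 sample precedes the first Part B dose (Table 2, footnote 2), so it reflects Part A treatment only. With about 90 patients allocated 1:1:1 (Section 6.1):

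- dupilumab in Part A: 2/3 × 90 = 60
- placebo in Part A: 1/3 × 90 = 30

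Assuming adequate assay sensitivity, drug present in serum after baseline separates the 60 from the 30. That is a randomization assignment, which paragraph 1 protects.

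**4. Would they reveal the Part B arm?**

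- *About 60 patients on dupilumab in Part A (60/90 = 67%).* They keep their exposure arm in Part B, and the two arms are designed to approximate different adult trough levels (Section 3.2.2). The level may therefore point to the current arm. How well it does so cannot be computed: doses are redacted and no concentrations are given.
- *About 30 patients on placebo in Part A (30/90 = 33%).* Their Part B regimen follows the exposure group assigned at randomization (Section 8.1). Part A concentrations carry no information on it. Their Part B samples stay closed until the Part B lock under either rule.

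**5. Does Section 11.4.9 close the gap?** Not as described. The restrictions it lists are on treatment allocation and site-level results. It does not name patient-level concentration, antibody, histology or biomarker data.

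**The case against.** The strongest reply is that the rules can be obeyed together by applying the stricter one. Paragraph 4 lifts one bar and orders no release. If concentrations reveal treatment, they count as unblinded data under paragraph 2 and stay closed to day-to-day personnel until the Part B lock. The dissemination plan, which is not shown, may also cover them.

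Part of this stands: the text permits access and does not direct it, and a careful reader could reach the intended result. But paragraph 4 is the specific rule for these data, and someone setting access rights from it could properly open them at the Part A lock. A rule on blinding should not depend on the reader noticing that another paragraph overrides it.

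Three stronger readings are tempting, and the document does not support them.

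- *That the last paragraph unblinds Part B for all 90 patients.* It cannot do so for the roughly 30 former placebo patients, and for the other 60 or so the degree is unknown.
- *That early release is certain.* The Part A analysis is optional in the text. Although it was evidently done, neither the lock dates nor the amount of Part B then remaining is stated. The 36 weeks of Part B is only an upper bound for the last patient, because the lock must follow that patient's week 16 visit.
- *That the trial's main result is compromised.* If performed, the week 16 analysis is final at that point (Section 6.2). Sites remain barred from these results during both periods, and histology and endoscopy scores are read centrally. Part B has no formal hypothesis or multiplicity control (Sections 11.1 and 11.4.4).

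Influence through queries or medical advice is possible, but nothing in the document shows that it occurred.

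**Conclusion.** The inconsistency is real and lies within one section. As written, the last paragraph of Section 8.7 permits the sponsor's blinded team to see patient-identified Part A results at the Part A lock, where the paragraphs above it keep the blind through Part B or to the Part B lock.

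If Part A is locked while Part B runs, and the assay is sensitive enough, the wording exposes the Part A assignment (active or placebo) of about 90 patients. For about 60 of them it may also hint at the current exposure arm, to a degree the document does not allow anyone to quantify. For about 30 it says nothing about the current arm. The consequence is confined to the integrity of blinded, mainly descriptive Part B safety and efficacy data; the week 16 primary analysis is not affected. This should be corrected, but it does not threaten the trial's primary conclusion.

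**What to change.** In the last paragraph of Section 8.7, replace 'for the respective study part' with 'for Part B'. Add that, between the Part A and Part B locks, patient-identified Part A drug concentration, anti-drug antibody, histology and biomarker results are available only to the separate primary-analysis team named in the dissemination plan. Name the same data in Section 11.4.9 so that the plan covers them explicitly.

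The cost is a phrase and a sentence in Section 8.7, a matching mention in Section 11.4.9, and the corresponding data-access settings. No procedure, sample size, timeline or patient burden changes.

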# 8.8. Emergency Unblinding (Applies to Part A and Part B only)

Unblinding of treatment assignment for a patient may be necessary due to a medical emergency or any other significant medical event (eg, pregnancy) and when a treatment decision is contingent on knowing the patient's treatment assignment. Study drug will be discontinued for patients whose treatment has been unblinded (Section 8.4.2):

- If unblinding is required:
  - Only the investigator will make the decision to unblind the treatment assignment.
  - Only the affected patients will be unblinded.
  - The designated study pharmacist(s)/designee at the study site will provide the treatment assignment to the investigator. If there is no study pharmacist, the investigator for the site will unblind the patient. Unblinding is performed using the IVRS/IWRS which will notify Regeneron.
  - The investigator will notify Regeneron and/or designee as soon as possible after unblinding the patient.

Treatment assignment is not to be provided to site personnel, other than the unblinded study pharmacist (when applicable), at any time during the conduct of the study, except in the case of a true emergency and when a treatment decision is contingent on knowing the patient's treatment assignment. In the event that there is no study pharmacist, the individual at the site fulfilling that role will be the only unblinded member of the site personnel.

## 8.9. Treatment Logistics and Accountability

#### 8.9.1. Packaging, Labeling, and Storage

A medication numbering system will be used to label blinded investigational study drug. Lists linking medication numbers with product lot numbers will be maintained by the groups (or companies) responsible for study drug packaging. In order to maintain the blind, these lists will not be accessible to individuals involved in study conduct. Part C study drug will be labeled with dupilumab.

Study drug will be stored at the site at a temperature of 2°C to 8°C; storage instructions will be provided in the pharmacy manual.

## 8.9.2. Supply and Disposition of Treatments

Study drug will be shipped at a temperature of 2°C to 8°C to the investigator or designee at regular intervals or as needed during the study. At specified time points during the study (eg, interim site monitoring visits), at the site close-out visit, and following drug reconciliation and documentation by the site monitor, all opened and unopened study drug will be destroyed on site after sponsor approval or returned to the sponsor or designee.

Regeneron Pharmaceuticals, Inc.

#### 8.9.3. Treatment Accountability

All drug accountability records must be kept current.

The investigator must be able to account for all opened and unopened study drug. These records should contain the dates, quantity, and study medication

- dispensed to each patient
- returned from each patient (if applicable), and
- disposed of at the site or returned to the sponsor or designee.

All accountability records must be made available for inspection by the sponsor and regulatory agency inspectors; photocopies must be provided to the sponsor at the conclusion of the study.

#### 8.9.4. Treatment Compliance

All drug compliance records must be kept current and made available for inspection by the sponsor and regulatory agency inspectors.

## 8.10. Concomitant Medications and Procedures

Any treatment administered from the time of informed consent/assent to final study visit will be recorded. Any treatment administered from the time of first dose of study drug to the final study visit will be considered concomitant treatment. This includes medications that were started before the study and are ongoing during the study.

#### 8.10.1. Prohibited Medications and Procedures

Treatment with the following concomitant medications is prohibited through week 52 and may result in temporary or permanent discontinuation of study drug (see Section 8.4.2). While the investigator may suspend study treatment at any time, any change to study drug administration should be discussed with the medical monitor.

- Swallowed topical corticosteroids (may be used as rescue treatment for EoE) (Parts A and B only)
- Systemic corticosteroids (may be used as rescue treatment for EoE) (Parts A and B only)
  - NOTE: One-time use of a corticosteroid as a part of the anesthetic preparation used during each endoscopy procedure is also allowed.
- Systemic immunosuppressive/immunomodulating drugs (including, but not limited to, mepolizumab, omalizumab, cyclosporine, mycophenolate-mofetil, azathioprine, methotrexate, IFN-γ, or other immunomodulatory biologics)
- Treatment with an investigational drug (other than dupilumab)
- For Parts A and B: Initiation, discontinuation, or change in dosage regimen after baseline of the following medications (stable doses of these medications are allowed):
  - Proton pump inhibitors

- Systemic leukotriene inhibitors
- For Parts A and B: Initiation, discontinuation, or change in dosage regimen of nasal and/or inhaled corticosteroids within 8 weeks prior to visit 2, visit 8, or visit 17 endoscopies with biopsies
- Initiation of SCIT, or change in dose for those patients on a stable dose of SCIT, within 1 year prior to screening (For Parts A and B only)
- SLIT, OIT, or EPIT (For Parts A and B only)
- Treatment with a live (attenuated) vaccine, eg:
  - Chickenpox (varicella)
  - FluMist-influenza
  - Intranasal influenza
  - Measles (rubeola)
  - Measles-mumps-rubella combination
  - Measles-mumps-rubella-varicella combination
  - Mumps
  - Oral polio (Sabin)
  - Oral typhoid
  - Rubella
  - Smallpox (vaccinia)
  - Yellow fever
  - Bacille Calmette-Guerin
  - Rotavirus
  - Varicella zoster (shingles)

The following concomitant procedures are prohibited during study treatment (for Parts A and B):

- Major elective surgical procedures
- Esophageal dilation (may be used as rescue procedure)
- Initiation or change of food-elimination diet regimen

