# 6. STUDY DESIGN

# 6.1. Study Description and Duration

This is a phase 3, multicenter, randomized, 3-part, double-blind, placebo-controlled study investigating the efficacy, safety, tolerability, PK, and immunogenicity of dupilumab in pediatric patients (ages  $\geq 1$  to <12 years) with active EoE.

Approximately 90 patients will be randomized (1:1:1 ratio for higher exposure dupilumab group: lower exposure dupilumab group: placebo) at approximately 30 study sites globally. The dosing of the placebo group will be matched with higher exposure and lower exposure dupilumab regimens in the respective weight tiers and placebo with different dosing will be combined. The details on the randomization will be specified in an interactive voice/web response system (IVRS/IWRS) requirement document.

This study consists of a screening period of up to 85 days, a double-blind 16-week treatment period (Part A), a 36-week extended active treatment period (Part B), a 108-week open-label extension period (Part C) and a 12-week follow-up period. The open-label extension period (Part C) will add up to 108 weeks of open-label treatment or until dupilumab becomes commercially available in the country of the participating patients (whichever comes first).

The study flow diagram is provided in Figure 1.

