- 16. Planned or anticipated use of any prohibited medications and procedures during the study
- 17. Planned or anticipated major surgical procedure during the study
- 18. Treatment with a live (attenuated) vaccine within 4 weeks before the baseline visit

NOTE: For patients who have vaccination with live, attenuated vaccines planned during the course of the study (based on national vaccination schedule/local guidelines), it will be determined, after consultation with a pediatrician, whether the administration of vaccine can be postponed until after the end of study, or preponed to before the start of the study, without compromising the health of the patient:

- Patients for whom administration of live (attenuated) vaccine can be safely postponed would be eligible to enroll into the study
- Patients who have their vaccination preponed can enroll in the study only after at least 4 weeks following administration of the vaccine
- 19. Active parasitic infection or suspected parasitic infection, unless clinical and (if necessary) laboratory assessments have ruled out active infection before randomization
- 20. Chronic or acute infection requiring treatment with systemic antibiotics, antivirals, or antifungals within 2 weeks before baseline visit

NOTE: Patients may be re-screened after the infection resolves

21. Known or suspected immunodeficiency disorder, including history of invasive opportunistic infections (eg, tuberculosis [TB], non-tuberculous mycobacterial infections, histoplasmosis, listeriosis, coccidioidomycosis, pneumocystosis, aspergillosis) despite infection resolution, or otherwise recurrent infections of abnormal frequency, or prolonged infections suggesting an immune-compromised status, as judged by the investigator

NOTE: Tuberculosis testing will be performed on a country-by-country basis according to local guidelines if required by regulatory authorities or ethics committees (ECs).

- 22. Known history of human immunodeficiency virus (HIV) infection or positivity for Hepatitis B or Hepatitis C antigens
- 23. On current treatment for hepatic disease including but not limited to acute or chronic hepatitis, cirrhosis, or hepatic failure, or has evidence of liver disease as indicated by persistent (confirmed by repeated tests ≥2 weeks apart) elevated transaminases (alanine aminotransferase [ALT] and/or aspartate aminotransferase [AST]) more than 3 times the upper limit of normal [ULN] during the screening period)

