#### 8.10.2. Permitted Medications and Procedures

Other than the prohibited medications listed in Section 8.10.1, treatment with concomitant medications is permitted during the study. If there is any question regarding whether a concomitant medication may be used during the study, the study site should contact the medical monitor.

Regeneron Pharmaceuticals, Inc.

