#### 8.10.3. Restricted Medications and Procedures during the Follow-Up Period

Patients may receive the prohibited medications/procedures listed in Section 8.10.1 as needed during the follow-up period, with the exception of live (attenuated) vaccine, which should not be used within 3 months after the last dose of study drug. Investigators are advised to prescribe prohibited medications/procedures judiciously, only when they are absolutely required for the appropriate management of study patients.

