- 15. The Pediatric Eosinophilic Esophagitis Symptom Score (PEESS) version 2.0 will be completed by caregivers of patients ≥1 to <12 years of age (determined at the time of screening visit 1).
- 16. Exit interviews will be conducted by a trained interviewer by telephone within 14 days of completing week 16/visit 8. These interviews will be completed with caregivers. Patients aged ≥8 to <12 years old (determined at the time of screening visit 1) may also join a portion of the exit interview.

#### 9.1.1.2. Footnotes for Table 2

- 1. This visit is the same as the week 16 visit for the double-blind study portion (Table 1), and all other assessments indicated for week 16 (Table 1) should be performed. Endoscopy with biopsies at visit 8/week 16 must be completed prior to administration of study drug for Part B Extended Active Treatment.
- 2. Study assessments will be performed, and blood samples will be collected prior to administration of study drug. In the event of suspected SAEs, such as anaphylaxis or hypersensitivity, functional dupilumab PK sample and anti-dupilumab antibody sample may be collected at or near the event.
- 3. In addition to predose assessments, AEs and vital signs (body temperature, blood pressure, respiratory rate, and heart rate) will be assessed at 30 minutes (±10 minutes) post-dose.
- 4. 4a. Study drug administration will continue through week 50.

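### Ending the whole prohibited-medication list at week 52 leaves no stated live-vaccine ban during Part C dosing, although live vaccines are barred for 3 months after the last dose

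*Protocol*

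**What the plan says.** Section 8.10.1 of the protocol introduces its list of medications with "Treatment with the following concomitant medications is prohibited through week 52 and may result in temporary or permanent discontinuation of study drug". The list has nine medication items. Some carry a limit to the first two parts, for example "SLIT, OIT, or EPIT (For Parts A and B only". The vaccine item, "Treatment with a live (attenuated) vaccine, eg", carries none. Its examples include the measles-mumps-rubella and varicella vaccines.

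Section 8.10.2 adds: "Other than the prohibited medications listed in Section 8.10.1, treatment with concomitant medications is permitted during the study". Section 8.10.3 allows the 8.10.1 medications as needed in the follow-up period, "with the exception of live (attenuated) vaccine, which should not be used within 3 months after the last dose of study drug".

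On timing, section 6.1 says that Part C "will add up to 108 weeks of open-label treatment". For Part B, footnote 4a to Table 2 says: "Study drug administration will continue through week 50". The note to exclusion criterion 18 (section 7.2.2.1) requires a decision, for children with a planned live vaccine, on "whether the administration of vaccine can be postponed until after the end of study, or preponed to before the start of the study".

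**The concern.** The week 52 limit fits a study that ends dosing with Part B. With Part C added, dosing runs well past the date on which the list lapses, while the follow-up rule still counts from the last dose. A site following the text would find live vaccines barred before Part C, not expressly barred while the child is being dosed in Part C, and barred again once dosing stops.

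Participants enter at 1 to under 12 years of age, and the exclusion 18 note itself expects some to have live vaccines due under national schedules. Part C is the longest dosing period, so a site may well have to decide whether such a vaccine can be given. What is at stake is a clear safety rule for open-label treatment.

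**Working it through.** No statistical formula applies. The check is a timeline, a count of list items and a comparison of sections.

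**Timeline** (durations from section 6.1, last Part B dose from footnote 4a to Table 2):
- End of Part B: 16 + 36 = week 52.
- End of Part C at the latest: 52 + 108 = week 160.
- Three months in weeks: 3 × 365.25 / 12 / 7 = 13.0.

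**Patient who leaves after Part B.** Section 8.10.1 bars live vaccines through week 52. Section 8.10.3 bars them from the last dose, week 50, to week 50 + 13.0 = 63.0. The two periods overlap, so there is no gap. The 12-week follow-up ends at 52 + 12 = week 64. For this patient the rules are coherent.

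**Patient who completes Part C without interruption.**

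| Period | Dosing | Stated rule on live vaccines |
|---|---|---|
| Weeks 0 to 52 | Yes | Prohibited (8.10.1) |
| Weeks 52 to 160 | Yes | No stated prohibition |
| About 13 weeks after last dose | No | Barred (8.10.3) |

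The gap is up to 160 − 52 = 108 weeks. It is shorter if Part C ends early for a patient. Re-entry patients start Part C after an interval off study, so their calendar differs, but they too are past week 52 of the study schedule.

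**Count of the 8.10.1 medication items** (leukotriene inhibitors counted with PPIs under the stable-dose item):
- Limited to Parts A and B: swallowed topical corticosteroids; systemic corticosteroids; PPI or leukotriene-inhibitor changes; nasal or inhaled corticosteroid changes; SCIT; SLIT, OIT or EPIT. That is 6.
- Not limited: systemic immunosuppressants or immunomodulators; investigational drugs; live vaccines. That is 3.
- Total: 6 + 3 = 9.

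Parts A and B end at week 52, so once the lead-in has set that limit for the whole list, the six tags add nothing. Tagging only some items has a purpose only if the other three were meant to continue.

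**Signs of intent elsewhere.** Section 8.2 separately lets patients adjust PPI use in Part C, which matches the tag on the PPI item and suggests the tagging was deliberate. Section 8.10.3 releases the listed medications at follow-up, which presupposes that they were restricted until then. The exclusion 18 note defers planned live vaccines to after the end of study. It is a Part A entry criterion and does not govern Part C, but it points the same way. None of the four criteria in section 7.2.2.2, which govern entry to Part B and uninterrupted entry to Part C, mentions vaccines.

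**The case against.** The strongest reply is that the protocol never says live vaccines are allowed in Part C. Section 8.10.2 withholds its permission from the medications listed in 8.10.1, and live vaccine is listed there, so it can be read as giving no permission at any time. That reading is fair. A reader might infer that the protocol expressly permits live vaccination during Part C, and the text does not support that. But the reading sits beside a lead-in that ends the prohibition at week 52, and a site has no rule for choosing between them.

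A second reply is that the tags do not contradict the lead-in. This is right: both give the same end date, so the tags are redundant, and what they reveal about the untagged items is inference.

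A third is that sites have a query route. Section 8.10.2 sends questions to the medical monitor, and section 8.4.2.2 requires contact if a prohibited medication is needed at any time in the study. This lowers the risk of a wrong decision. It does not correct the text: the first route works only if the site sees a question, and the second depends on the vaccine being prohibited, which is the status in doubt.

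Finally, the protocol gives no data on the risk of live vaccination under dupilumab, so a claim of harm would have no support here. That stands in full.

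**Conclusion.** The point holds as an incoherent safety rule. For up to 108 weeks of Part C dosing the protocol states no live-vaccine ban, and it then bars live vaccines for about 13 weeks after the last dose. This rests on reading the lead-in as governing the whole list, which is its plain sense. The gap arises only in Part C.

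The documents do not show harm and do not give the number of children affected. A reader might also infer that immunosuppressants and investigational drugs are freely allowed in Part C. That does not follow: their status is unclear by implication only, and the sponsor has to state it. The week 16 primary and secondary analyses are unaffected.

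**What to change.** Reword the lead-in of section 8.10.1 so that the week 52 limit applies only to the six items tagged Parts A and B, and add a sentence such as: *Live (attenuated) vaccines are prohibited throughout study treatment, including Part C, and until 3 months after the last dose (Section 8.10.3).* This gives the tags a function and joins 8.10.1 to 8.10.3 without a gap. In the same edit the sponsor should state whether systemic immunosuppressants or immunomodulators and investigational drugs also remain prohibited in Part C.

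Repeating the exclusion 18 postponement check at Part C entry would be a sensible option, but the correction does not depend on it.

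The cost is a short text change, with no effect on sample size or analysis. The real downside is that live vaccination is deferred for up to 108 more weeks in patients who continue. If the sponsor does not intend that, it should state the opposite rule for Part C explicitly and reconcile it with section 8.10.3.
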